
Our lab group has assessed the age of diagnosis and age of appropriate intervention in children with hearing loss in Kentucky. We have identified a statistically significant delay in diagnosis and treatment for patients from the Appalachian region of Kentucky. We are also examining the causative factors behind this delay. The lack of education and family support is a common theme in families that fail to follow-up or are delayed in their follow-up. We are proposing a study to examine the effect of a patient navigator to influence patient satisfaction, patient/family behavior and the age of diagnosis of pediatric hearing loss

2. Objectives:

Hypothesis: The assistance of a patient navigator for families with a newborn who failed a newborn hearing-screening test will result in improved patient compliance, patient satisfaction, and age of diagnosis and intervention of pediatric hearing loss.

Specific Aim 1: Examine the effect of a patient navigator to influence the age of diagnosis and intervention for pediatric hearing loss.

Specific Aim 2: Examine the effect of a patient navigator to influence patient satisfaction, knowledge, and compliance with the hearing evaluation and intervention process following newborn hearing screening.

Form B: Medical IRB Research Description

3. Study Design:

For Specific Aim 1, mothers of newborns failing birth hearing screening will be recruited. Participants will be placed into Appalachian and non-Appalachian stratum and then randomized into a patient navigator group or the standard of care group. The navigator group will receive an intervention consisting of educational support from a patient navigator. We will compare the non-adherence rates to obtain the recommended testing within 3 months between groups and strata. The timing of testing will also be assessed and compared between regional strata. At enrollment, we will collect data on maternal socioeconomic status, educational level, and distance from testing center and infant health. Findings will be correlated with adherence to follow-up and timing of services. If the child receives follow up before 3 months and it is determined that child has hearing loss he or she will be approached by a research staff member to participate in the second part of the study (Aim 2) to be randomized and either followed for one year by the patient navigator or to follow standard of care practice.

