Specific Aim 1: The same outcomes will be measured in both groups. Group 1 will be contacted every 2 weeks after discharge from the hospital regarding their child who failed the newborn hearing screen by the patient navigator. This contact will primarily occur through phone calls, but can also occur through email or text messages on a password protected phone if the patient prefers one of these communication methods. Communications between the patient and patient navigator will consist of inquiring on the health and development of the child, addressing questions about hearing, hearing loss, upcoming tests, and intervention services. The navigator will attempt to have these questions answered by clinical staff involved in the patients care and will communicate this to the family. Group 2 will not have navigator contact but will work directly with their hearing healthcare clinic and other referral centers for diagnostic and intervention services (THIS IS THE CURRENT STANDARD OF PRACTICE). Parents in each group of the children born at UKMC, children born at outside facilities (and referred to UKMC Audiology clinic for follow up testing), and children referred to CSHCN for follow up testing will be given a standard brochure that contains basic information about newborn hearing screening and a contact number regarding obtaining further assistance with the diagnostic testing and/or treatment. This is document produced and circulated by the state of Kentucky childhood early hearing detection and intervention agency (SEE APPENDIX 1). At the time of enrollment, parents of the child with the failed hearing screening will fill out a questionnaire which assesses patient satisfaction, knowledge, attitudes, and behaviors, along with some demographic information (**see attached**) from both groups. The subjects who are discharged from outside facilities will have the questionnaire completed by mail, email (through REDCap), or phone with the research staff member. Notes from phone conversations from navigator phone calls will be recorded by the navigator and then recorded on an excel spreadsheet. The data from the questionnaire and the other time points will also be recorded on an excel spreadsheet. At the follow up appointment the research team will also collect data on the outcome of the diagnostic testing. If subjects do not receive their diagnostic follow up within the 3 month time frame

Form B: Medical IRB Research Description

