a member of the research team will contact them by phone in order to complete the exit questionnaire and determine if they had diagnostic follow-up at another facility. If the patient cannot be reached by phone the UK research team will work collaboratively with CSHCN to find out (through the EHDI system) if these patients received follow up care in another clinic outside of the study or if they were lost to follow up. This data will be kept in a password-protected file on a password-protected computer and along with the consents will be kept in the locked office of the PI. This data will be kept for a total of 6 years after the conclusion of the study.

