The study does not require any special space. A patient navigator is not a care provider but is an advocate for patients to identify concerns or questions and to help patients navigate through the healthcare system. A phone in a private area of the Audiology clinic will be utilized with an encrypted, password protected computer for data collection and entry. The patient navigator has specialized skill to work with families who have a child with hearing loss and follows Good Clinical Practice when speaking with families. Research staff have experience and training in clinical research and utilize the principles of Good Clinical Practice when screening and enrolling. All have completed appropriate and documented Human Subjects Protection training.

8. Potential Risks and Safety Precautions:

The challenges present in this study relate to the Belmont report issues of respect for persons, beneficence, and justice. The respect for persons becomes an issue in that we are studying children and they are naturally a vulnerable population. A major concern in diagnosing and managing children with hearing loss is that they are lost to follow-up after they leave the hospital. In order to gain access to these children, we need to recruit them while they are in the hospital and approaching them about the study may produce pressure to participate. There is a risk of coercion in this setting. To prevent this coercion, the PI (who could potentially be involved in the patient's care) will not consent the patient or have contact with the patient's family during study Aim 1. The issue of beneficence also comes when dealing with children with hearing loss. If there is miscommunication or misunderstanding of the parents about the information presented or mistrust of the navigator or research team, then this may lead the family further away from the appropriate diagnostic and treatment resources. There are natural safeguards against this as the state of Kentucky monitors failed newborn hearing screening and

Form B: Medical IRB Research Description

independently and families are contacted by the state until they are seen in follow-up. There is also a risk of breach of confidentiality, as we will be contacting this family and interacting with other hearing professionals involved in the care of the child with hearing loss.

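### For Aim 1 families with no known test at 3 months, the source of the outcome depends on whether the parent can be reached by phone, which can differ by arm; the size and direction of any bias are unknown

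*Combined protocol and SAP*

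**What the plan says.** Section 3 (Study Design) states the Aim 1 comparison: "We will compare the non-adherence rates to obtain the recommended testing within 3 months between groups and strata". The opening section on sample size and recruitment powers the trial on this outcome. The documents never call it primary, but no other outcome in the available text has a sample-size calculation.

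Section 6 (Research Procedures, Specific Aim 1) gives three sources in order.

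1. Clinic data: "At the follow up appointment the research team will also collect data on the outcome of the diagnostic testing".
2. The trigger for the next source is "If subjects do not receive their diagnostic follow up within the 3 month time frame". A research team member will then "contact them by phone in order to complete the exit questionnaire and determine if they had diagnostic follow-up at another facility".
3. The state record, only after the phone call fails: "If the patient cannot be reached by phone the UK research team will work collaboratively with CSHCN to find out (through the EHDI system"). This look-up separates care at another clinic from loss to follow-up.

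The same section describes the contrast in contact: "Group 1 will be contacted every 2 weeks after discharge from the hospital", primarily by phone, while Group 2 has no navigator contact. Section 8 adds that the state monitors failed screens on its own and that "families are contacted by the state until they are seen in follow-up".

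The sample-size section treats families who go outside UK for testing as possible leavers and allows 20% dropout for this.

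**The concern.** The rule is the same on paper in both arms, but it branches on something that happens after randomization: whether the parent answers the phone. A reached parent is classified from what he or she says. An unreached parent is classified from a state record. The intervention is itself a series of phone contacts about matters that include upcoming tests, so it can change how often parents are reached and what they say when asked. Parents know their arm, and no blinding of the caller is described.

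The families affected are those with no known test, which is the group that supplies the non-adherence events. If errors in the two sources differ and the mix of sources differs by arm, the comparison can be biased even though each arm follows the same written procedure. Bias one way inflates the false-positive rate of the one-tailed test; bias the other way costs power.

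**Working it through.** **Inputs from the sample-size section.** Control non-adherence 27% (Appalachian) and 15% (non-Appalachian); navigator 12% and 6%; 226 evaluable, of whom 90 are Appalachian and 136 are not; one-tailed CMH test at 0.05; 80% power. Allocation is not stated, so 1:1 within stratum is assumed: 45 and 68 per arm.

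**Reproducing the plan's figure.** With n per arm in a stratum and CMH weight w = n/2, the weights are 22.5 and 34.

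- Weighted difference: 22.5 × 0.15 + 34 × 0.09 = 6.435.
- Null SD, √Σ w² p̄(1−p̄)(2/n), with p̄ = 0.195 and 0.105: √(3.532 + 3.195) = 2.594.
- Alternative SD, √Σ w² [p₁(1−p₁) + p₂(1−p₂)]/n: √(3.405 + 3.126) = 2.556.
- Power: Φ((6.435 − 1.645 × 2.594)/2.556) = Φ(0.849) = 80.2%.

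This matches the stated 80%. A simulation of the CMH test without continuity correction gives about 81%.

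**How many events are in play.** At control rates, 45 × 0.27 + 68 × 0.15 = 22.4 non-adherent families per arm. Reclassifying a few of them moves the result.

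**Illustration of differential misclassification.** Let f be the share of all truly untested families in an arm that end up recorded as tested. Then apparent rate = true rate × (1 − f). The values of f are assumptions; the documents give none.

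*No true effect (27% and 15% in both arms):*

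| f navigator | f control | Apparent rates, navigator | Apparent rates, control | One-tailed rejection |
|---|---|---|---|---|
| 0 | 0 | 27.0%, 15.0% | 27.0%, 15.0% | 5% |
| 20% | 20% | 21.6%, 12.0% | 21.6%, 12.0% | 5% |
| 20% | 10% | 21.6%, 12.0% | 24.3%, 13.5% | 11% |
| 10% | 20% | 24.3%, 13.5% | 21.6%, 12.0% | 2% |

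For the third row, the weighted difference is 22.5 × 0.027 + 34 × 0.015 = 1.118, and Φ((1.118 − 1.645 × 2.786)/2.785) = Φ(−1.244) = 10.7%. Reversing the sign gives Φ(−2.047) = 2.0%. Simulation agrees with both.

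*Planned effect present (12% and 6% with the navigator):*

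| f navigator | f control | Power (simulated) |
|---|---|---|
| 0 | 0 | 81% |
| 0 | 10% | 69% |
| 0 | 20% | 54% |

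**What f stands for.** Unreached families are classified from EHDI, so f = (share reached) × (false-report rate among those reached). If 60% are reached in both arms and 30% versus 10% of them misreport (all assumed), f is 0.6 × 30% = 18% versus 0.6 × 10% = 6%, and rejection with no true effect is about 12%.

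**If a reported outside test removes the family** instead of scoring it as adherent, the 20% versus 10% case gives about 9% instead of 11%. The distortion is smaller but does not vanish.

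**The case against.** A reader might infer that an unverified parental statement, test date included, decides the primary outcome, that it favours the navigator arm, and that it makes a false-positive result likely 20% to 35% of the time. The documents do not support that reading.

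- **Scoring.** Section 6 says only that the call will "determine if they had diagnostic follow-up at another facility". It does not say that a reported outside test counts as adherence, or that the parent's date settles the 3-month limit. The sample-size section points instead to such a family leaving the study.
- **Verification.** None is described, but none is excluded. Section 8 foresees contact with other hearing professionals involved in the child's care, and part of the protocol is not in the available text.
- **Direction.** Misreporting could be lower with a navigator, who discusses upcoming tests with the family and keeps notes of the calls, so a false claim is easier to notice. The 3-month caller is a research team member, not stated to be the navigator.
- **Size.** Rejection rates of 21% and 35% do follow arithmetically from shares of 30% or 40% versus 10%, but only if those shares apply to all untested families, although the unreached ones are classified from EHDI.
- **Scope.** Data collection at the follow-up appointment covers families tested as planned. Only those with no known test are affected.

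All of these points stand, and they limit what can be claimed. They do not remove the core: the order of sources is written into the plan, and it branches on a variable that the intervention can affect. Under either scoring, the phone answer helps settle the family's status, by taking away an event or by taking the family out of the denominator.

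**Conclusion.** The point holds as a risk of differential misclassification in the outcome that drives the sample size. It does not hold as a demonstrated bias in favour of the navigator. Modest assumed differences move the false-positive rate from 5% to about 11% in one direction or to about 2% in the other, and false reports confined to controls lower power from about 81% to 69% or 54%. Equal false-report shares leave the false-positive rate at 5%. All of these figures rest on assumed shares, 1:1 allocation and scoring of reported outside tests as adherent; the true size and sign cannot be derived from the documents. The sample size of 226 reproduces and is not in dispute. The change is worth making because the plan already has a route to a record that does not depend on the parent answering the phone.

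**What to change.** Amend section 6 (Specific Aim 1) as follows.

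- At a fixed time after the 3-month limit, look up every randomized child without a study-clinic test record, and ideally every randomized child, in EHDI or the testing clinic's record, whether or not the parent was reached. Existing staff can do this, preferably from a list that does not show arm.
- Define adherence in both arms from the recorded test date.
- Use the parent's phone report to locate a missing record and in a sensitivity analysis.
- State that a documented timely test at an outside facility is scored the same way in both arms, and reconcile this with the sample-size section, which treats testing outside UK as leaving the study.

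The cost is a short protocol change and look-ups for at most about 284 children through the CSHCN collaboration already planned. Whether that arrangement permits whole-cohort queries is not stated and should be confirmed. The main downside is that some outside tests may be late or missing in EHDI, whose completeness the documents do not give. The plan already accepts that limitation for unreached families.

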For Specific Aim 2, mothers of newborns will also be recruited and randomized to navigator vs. no navigator, but this Aim focuses on the diagnosis of hearing loss after the child has had two failed outpatient audiological tests. At the time of hearing loss diagnosis, these participants will be stratified and then randomized similar to Aim 1 into trial arms. Patients will be randomized into 2 groups. Group 1 will have contact with the navigator from the time of hearing loss diagnosis until the first year of life while group 2 will not have the navigator (STANDARD PRACTICE).

4. Study Population and Subject Recruitment Methods and Privacy:

Specific Aim 1: This portion of the study will involve infants born at the University of Kentucky Medical Center, infants born at outside facilities and their families (that are referred to UKMC Audiology Clinic for follow-up testing), and infants and families that are referred to the Commission for Children with Special Health Care Needs (CCSHCN) for follow-up testing. Children that are born at UK undergo newborn hearing screening using a test called ALGO. This test is performed on infants who are older than 34 weeks gestation, have normal external ear, are not on any stimulants, and are in a sleeping or relaxed state approximately 24 hours after birth. This is an automated test that is performed as standard of practice and the results of the test are listed as "PASS" or "REFER." When a child has a "REFER" result then the postpartum nurses or clerk calls the UK ENT clinic (the office of the PI) prior to discharge from the hospital for scheduling a diagnostic hearing test as standard practice. At that point, the PI is an authorized care provider for the patient and that is how the subjects are identified.

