The parents will be verbally reassured that their participation or lack thereof will have no bearing on their or their child's care. The children who enroll in Aim 2 must meet the same inclusion criteria as Aim 1, except they also must be younger than 6 months old and have a final diagnosis of hearing loss. We expect to enroll 62 subjects, with 31 children from the Aim 1 enrollment and 31 from identified clinic patients who are seen in the Audiology clinic for follow up hearing tests. For this Aim there again will be no discrimination on age, gender, or ethnicity; however, the parents must be able to speak English or Spanish, as that will be the primary means of communicating with the patient navigator.

Patients who previously received navigation in Aim 1 will also be approached by a research staff member after a hearing loss diagnosis is given. These patients will also be consented again for Aim

Form B: Medical IRB Research Description

2 of the study, but they will continue to receive navigation instead of being randomized a second time. This group of patients will also be followed in the study for 12 months.

5. Informed Consent Process:

Aim 1: At the time of the failed ALGO test, the nurse administering the test will give an information letter to the parents of the child who fails the newborn hearing test. As standard practice, the newborn nursery staff calls our clinic to schedule diagnostic hearing testing. That is how a prospective research subject is identified. At that time our research staff will go to the patient room to talk with the parents about the study. A member of the research staff who is authorized to obtain consent will come to inpatient hospital room to discuss the study and obtain consent.

Subjects who have a child who failed the newborn hearing in another facility will be contacted by phone once they have an outpatient hearing screening test (ABR) scheduled. They will have an informed consent by phone through a member of the research staff and will have opportunity to discuss study and ask questions.

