Specific Aim 2: The same outcomes will be measured in both groups, but this Aim will focus on the timing of intervention from the hearing screening as an outpatient. The patients randomized to the navigator group will be contacted weekly-biweekly to provide educational and psychosocial support of participants with the same four conversation points from Aim 1. The testing that diagnosed hearing loss will be recorded into the EHDI database. At the time of enrollment, parents of the child with the failed hearing test will also fill out a questionnaire which assesses patient satisfaction, knowledge, attitudes, and behaviors, along with some demographic information (**see attached**) from both groups (navigator and non-navigator). We will have the patients complete the questionnaire at enrollment and 12 months after enrollment. We will also record the age of initial diagnostic test at their hearing healthcare clinic (depending on where the patient received diagnostic testing), age of definitive diagnosis of hearing loss, age of early intervention consultation, age of hearing aid fitting, and (if patient meets criteria for cochlear implantation) age of cochlear implantation. Parent(s) of children in this Aim will also receive another questionnaire, similar to the one they receive at the beginning of Aim 2 that assesses patient satisfaction, knowledge, attitudes and behaviors with follow up demographic information during the one year follow up. Notes from phone conversations from navigator phone calls and data from the questionnaire and at the other time points will be recorded by the navigator and then recorded on an excel spreadsheet. This data also will be kept in a password-protected file on a password-protected computer and along with the consents will be kept in the locked office of the PI. This data also will be kept for a total of 6 years after the conclusion of the study.

7. Resources:

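### Aim 2 times intervention from before its own randomization and does not mark two ages already fixed at that point as baseline

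*Combined protocol and SAP*

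**What the plan says.** **Entry and randomization.** Section 3 (Study Design) places Aim 2 "after the child has had two failed outpatient audiological tests" and continues: "At the time of hearing loss diagnosis, these participants will be stratified and then randomized similar to Aim 1 into trial arms". The navigator group has "contact with the navigator from the time of hearing loss diagnosis until the first year of life". Section 4 (Study Population) adds that Aim 2 children must meet the Aim 1 criteria, except that "they also must be younger than 6 months old and have a final diagnosis of hearing loss".

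**Timing measures.** Section 6 (Research Procedures, Specific Aim 2) opens by saying that both groups have the same outcomes measured, and that "this Aim will focus on the timing of intervention from the hearing screening as an outpatient". It then says: "We will also record the age of initial diagnostic test at their hearing healthcare clinic", followed by "age of definitive diagnosis of hearing loss, age of early intervention consultation, age of hearing aid fitting" and, for eligible children, age at cochlear implantation. No line in the available text separates baseline ages from outcome ages, moves the time origin to randomization, or gives an Aim 2 analysis.

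**Who is randomized.** Section 4 expects 62 children, 31 of them from Aim 1. It also says that children navigated in Aim 1 stay on navigation and are not randomized again. Sections 3 and 5 describe children coming from Aim 1 as entering a randomized comparison.

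**The concern.** An arm comparison is easiest to interpret when its clock starts at randomization, because everything counted can then respond to the assigned arm. Here the stated origin comes earlier, and two of the five recorded ages are complete before the Aim 2 navigator makes contact.

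Two things are at stake. First, the Section 2 hypothesis claims an effect on age at diagnosis as well as at intervention. Unless the early ages are labelled, a difference between Aim 2 arms in age at diagnosis could be read as support for it. Among children newly randomized in Aim 2, such a difference can only be chance. Second, time that the navigator cannot influence widens the standard error of a comparison that has at most 62 children.

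**Working it through.** **The plan's own figure.** The only Aim 2 number is the expected enrolment of 62. It comes without alpha, power, effect size, SD or test, so it cannot be reproduced.

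**Order of events (Sections 3, 4, 6 and 8).** First outpatient test → second, confirming test and final diagnosis → consent and Aim 2 randomization → navigator contact → early-intervention consultation, hearing aid, implant. The stated clock starts at the first step. Ages start earlier still, at birth. Section 5 can be read as approaching parents at the initial clinic visit, but even then the initial test comes before randomization.

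**Bias or noise.** Write the measured time as A + D, where A is the time before randomization and D the time from randomization to the event. Randomization gives A the same expected distribution in both arms, so the expected arm difference is the effect on D. A adds variance only.

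**Size.** Let a and d be the SDs of A and D, assumed independent:
- variance share of A = a²/(a² + d²)
- SE from randomization ÷ SE with the earlier clock = d/√(a² + d²)

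All SDs below are assumptions. For age from birth, age at randomization is taken as uniform over 1-6 months (a = 5/√12 = 1.44) or 1.5-5 months (a = 3.5/√12 = 1.01). The only related limit in the documents is the 6-month entry ceiling.

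| Clock | a (months) | d (months) | Share of A | SE ratio | SE cut |
|---|---|---|---|---|---|
| Outpatient test | 0.5 | 1.5 | 0.25/2.50 = 10% | 0.95 | 5% |
| Outpatient test | 0.5 | 2 | 0.25/4.25 = 6% | 0.97 | 3% |
| Birth, entry 1.5-5 | 1.01 | 1.5 | 1.02/3.27 = 31% | 0.83 | 17% |
| Birth, entry 1.5-5 | 1.01 | 2 | 1.02/5.02 = 20% | 0.89 | 11% |
| Birth, entry 1-6 | 1.44 | 1.5 | 2.08/4.33 = 48% | 0.72 | 28% |
| Birth, entry 1-6 | 1.44 | 2 | 2.08/6.08 = 34% | 0.81 | 19% |

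**What this means for power.** Assume 31 per arm, two-sided alpha 0.05 and an effect of 0.72 SD of D, so that the clock from randomization gives 81%. With r = a/d, power is 72% at r = 0.5 and 52% at r = 1. The age-from-birth rows have r from 0.50 (1.01/2) to 0.96 (1.44/1.5). The outpatient-test rows have r of 0.25 to 0.33, so their power lies between 81% and 72%. With a correlation of 0.3 between A and D, power is 62% at r = 0.5 and 42% at r = 1.

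**How many are randomized.** If the children already navigated are counted among the 31 from Aim 1 and make up about half of them (both assumptions), 15 or 16 are not re-randomized. That leaves 62 − 16 = 46 or 62 − 15 = 47 in the randomized comparison.

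**The case against.** The strongest reply is that Section 6 is a data-collection section. Recording "age of definitive diagnosis of hearing loss" is not an error, and the proposed covariate adjustment needs it. The phrase about identical outcomes is generic and also appears under Aim 1. The stated focus of Aim 2 is intervention, and the origin phrase may only mark the phase of care. This stands in part: a reader might infer that the plan will test the two early ages between Aim 2 arms, but no available text says so. What remains is that the text separates nothing and names an origin before randomization.

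A second reply is that age is a legitimate scale. Section 1 adopts the JCIH recommendations as the study's standard, and their targets are ages: diagnosis before 3 months, amplification before 6, implantation by 12. Adjusting for age at diagnosis would recover most of the lost precision. This also stands. The available text plans no such adjustment.

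A third reply concerns the children carried over from Aim 1. Their ages at test and diagnosis follow Aim 1 randomization and can respond to the Aim 1 navigator. In the whole enrolled cohort, early-age differences could therefore be systematic. This stands, and it limits the point to children newly randomized in Aim 2.

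**Conclusion.** The point holds for children newly randomized in Aim 2. The order of events follows from the text alone. The size rests on assumed SDs and on independence of the two intervals: about 3-5% of the standard error for the clock that Section 6 states, and about 11-28% for unadjusted age from birth. It is worth correcting because the correction costs almost nothing.

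Three stronger readings are not supported:
- That the early clock biases the randomized comparison. It adds noise only.
- That the 11-28% loss applies to the outpatient-test clock. That clock carries only the gap from first test to confirmed diagnosis.
- That averaging age only over treated children could reverse the apparent benefit. Age at fitting does exist only for fitted children, and the available text has no rule for the others, but no analysis restricted to treated children is stated. This is an open risk, not a planned error.

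**What to change.** 1. For children randomized in Aim 2, define the timing outcomes as time from randomization to early-intervention consultation and to hearing aid fitting. For each outcome, keep every randomized child who has not already had the event, and censor those without it at the end of follow-up.
2. Label age at initial test and age at definitive diagnosis as baseline. Use age at diagnosis as a covariate, and do not present arm differences in either age as Aim 2 navigator effects.
3. Still report ages at intervention against the JCIH age targets in Section 1.
4. Analyse separately the Aim 1 navigator children who continue without a second randomization. Reconcile Section 4 with Sections 3 and 5 on who is randomized, and state how many of the 62 that leaves.
5. Reconcile the end of Aim 2 follow-up, which Section 3 ties to the first year of life and Sections 4 and 6 to 12 months in the study, so that the censoring date is defined.

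The cost is wording and a little more analysis. The event dates are already collected, the randomization date is inherent to the trial, and no further children are needed. The one trade-off is a main time scale that differs from the JCIH age scale, which item 3 covers.
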